1. PROTOCOL OVERVIEW

Protocol Title:	Baricitinib in relapsing giant cell arteritis (GCA): a phase II, single-institution, open-label pilot study
Study Chairs:	[name]. – Principal Investigator [name]. – Co-Principal Investigator
Statistician:	[name], M.S.
Study Coordinator:	[name], C.C.R.C.
Participating Sites:	Mayo Clinic, Rochester, MN
Activation Date:	1/1/2017
Sample Size:	15
Target Enrollment Period:	60 weeks
Study Design:	Open-label, Phase II
Primary objective:	To determine the safety and tolerability of baricitinib, 4mg oral daily, in GCA
Secondary objective	To gather preliminary data on the efficacy of baricitinib, 4mg oral daily, in patients with relapsing GCA 
 • Relapse-free survival at week 52 • Relapse-free survival at week 24 • Duration of glucocorticoid-free remission • Number of relapses per subject over time • Change from baseline erythrocyte sedimentation rate (ESR) to end of study • Change from baseline C-reactive protein to end of study • Glucocorticoid dose (mg) at week 52 compared to enrollment • Change in BVAS from baseline to end of study
Inclusion criteria	1. Diagnosis of GCA defined by the following Revised GCA Diagnosis Criteria: 
 • Age \geq50 years. • History of ESR \geq 50 mm/hour or CRP \geq 10 mg/L. • Presence of at least one of the following: 
 ○ Unequivocal cranial symptoms of GCA (new onset localized headache, scalp or temporal artery tenderness, otherwise unexplained mouth or jaw pain upon mastication). ○ Unequivocal symptoms of PMR, defined as shoulder and/or hip girdle pain associated with inflammatory stiffness. ○ Systemic inflammatory disease in which the presence of the fever ($>$38 degrees Celsius for \geq 7 days), weight loss ($>$ 5 lbs or 10% premorbid weight), and/or night sweats were attributable to GCA and no other cause was

	
identified.
 
● Presence of at least one of the following:
○ Temporal artery biopsy revealing features of GCA.○ Evidence of large-vessel vasculitis by angiography or cross-sectional imaging, including but not limited to magnetic resonance angiography (MRA), computed tomography angiography (CTA), positron emission tomography-computed tomography (PET-CT) or evidence of large-vessel or temporal artery vasculitis by ultrasound (US). 
2. Relapse with active GCA within 6 weeks of study entry where active disease is defined by an ESR ≥ 30 mm/hr or CRP ≥ 10 mg/L AND the presence of at least one of the following:
 
● Unequivocal cranial symptoms of GCA (new onset or recurrent localized headache, scalp or temporal artery tenderness, otherwise unexplained mouth or jaw pain upon mastication [i.e., jaw claudication]).● Unequivocal symptoms of PMR, defined as shoulder and/or hip girdle pain associated with inflammatory stiffness.● Other feature(s) judged by the clinician investigator to be consistent with GCA or PMR flares (e.g. fever of unknown origin, unexplained weight loss, fatigue/malaise, etc.) 
3. Clinically stable at baseline visit (study drug initiation) such that the subject is able to safely participate in the standardized taper regimen in the opinion of the investigator.
 
.

--	---

The purpose of this study is to evaluate the safety and tolerability of baricitinib in a population of patients with relapsing GCA. To accomplish this we will perform a single-institution, open-label pilot study assessing the safety and tolerability of baricitinib (4 mg daily, oral, for 52 weeks) in addition to a standardized glucocorticoid taper. It is anticipated that adjunct baricitinib will be safe and well tolerated by patients with GCA and demonstrate preliminary efficacy as measured by reducing inflammatory markers, decreasing steroid requirements and increasing relapse-free survival.

The vasculitis group at Mayo Clinic in Rochester, Minnesota is well-suited for this study with 50 years of GCA research experience accounting for over 200 publications in this condition. In addition, this institution has one of the largest referral and population-based GCA cohorts in North America and has successfully participated in three recent multicenter, international therapeutic clinical trials evaluating biologic agents in patients with GCA.

Primary Objective

To determine the safety and tolerability of adjunct baricitinib (4mg, oral daily, for 52 weeks) in combination with standardized glucocorticoid taper among patients with relapsing GCA.

Secondary Objective

To assess preliminary efficacy of adjunct baricitinib (4mg, oral daily, for 52 weeks) in combination with standardized glucocorticoid taper among patients with relapsing GCA.

3. BACKGROUND/SIGNIFICANCE

3.1. Giant Cell Arteritis

Giant cell arteritis (GCA) is the most common idiopathic systemic vasculitis in persons aged ≥ 50 years. There is a predilection for vascular inflammation in medium and large arteries with a particular tropism for the proximal aorta and its primary branches. Arterial inflammation leads to narrowing or occlusion from intimal hyperplasia and can have dramatic consequences. Specifically, ischemic cranial symptoms are considered a medical emergency due to the risk of transient or permanent visual loss, which can occur in up to 15-20% of patients with GCA [6, 12]. In addition, patients with GCA are at elevated risk of developing aortic complications (aneurysm, dissection, rupture) which can be associated with significant morbidity and mortality. Indeed, in a population-based study, patients with GCA were 17.3 times more likely to develop thoracic aortic aneurysm [13]. Furthermore, patients with GCA who develop aortic aneurysm and/or dissection have a near 3-fold increased mortality compared to non-GCA patients[14].

3.2. Glucocorticoids

Prompt initiation of high-dose glucocorticoids (GC) remains the cornerstone of treatment of GCA and delay in treatment initiation can increase the risk of severe ischemic complications [15]. Although highly variable, improvement of inflammation can occur within days to weeks, leading to dramatic reduction in inflammatory markers and systemic symptoms. After attaining remission, the GC dose is gradually decreased over a prolonged course of approximately 18-36 months. Nevertheless, within the first year of diagnosis approximately 50% of patients will experience a clinical relapse of the disease despite GC treatment [16]. Furthermore, GC treatment in the affected age-group is associated with a high number of adverse effects (AEs) including, but not limited to, infection, hypertension, diabetes, cataracts, glaucoma and osteoporosis. Such AEs have been reported in up to 90% of patients receiving GC for the treatment of GCA and the risk of AEs increases with the cumulative dose and duration of GC exposure [7, 17]. Therefore, glucocorticoid-sparing agents are greatly needed for both induction and maintenance therapy to decrease the frequency of GC-associated morbidity.

3.3. Glucocorticoid-sparing Agents

[figure not shown]
Many investigations have attempted to find a suitable replacement for GC for the treatment of GCA; however, no clear therapeutic agent has shown comparable efficacy or superiority to date. Among conventional immunosuppressive agents, methotrexate has been considered a reasonable second-line agent after GC in patients with severely active/relapsing disease or in patients with high risk for GC-associated adverse events. Nevertheless, small clinical trials evaluating methotrexate in GCA have only found a modest benefit in decreasing relapse risk and glucocorticoid dose reduction [18]. Limited or no benefit has been observed among other oral conventional immunosuppressive agents including leflunomide [19, 20], azathioprine [21] and mycophenolate mofetil [22]. Biologic agents, including tumor necrosis factor alpha inhibitors, have shown equally disappointing results [23-25].

3.4. Immunopathologic Studies

Lymphocytic infiltration in vascular lesions is largely driven by two T cell subsets: T helper type 17 (Th17) and T helper type 1 (Th1) cells [26, 27] (**Figure 1**). These T cell lineages appear to be stimulated by independent signals from different antigen presenting cells (APC) with Th17 cells requiring interleukin (IL)-1 β / IL-6 / IL-21 / IL-23, whereas the Th1 pathway is dependent on APCs secreting IL-12 / IL-18 and interferon gamma (IFN- γ) [27, 28]. In early untreated GCA, both T cell lineages are increased in the peripheral circulation as well as within vascular inflammatory infiltrates. The Th17 pathway appears to be very sensitive to treatment and GC

rapidly control the Th17 effector cytokine production of IL-1, IL-6, IL-17 and IL-23 with concomitant depletion of both circulating and infiltrating Th17 cells [26, 28].

FIGURE 1: Pathophysiology of giant cell arteritis

Despite the effective reduction of the Th17 pathway, a Th1 cell response persists in both biopsy and blood samples of treated patients with GCA [26]. The Th1 cytokine signature (IL-2 and IFN- γ) associated with chronic vasculitis in GCA is poorly susceptible to GC-mediated suppression [28]. Currently, multiple clinical trials investigating biologic agents targeting extracellular proinflammatory cytokines are underway [IL-6, tocilizumab and secukinumab; IL-12/IL-23, ustekinumab; IL-1, gevokizumab]. However, with the exception of ustekinumab, these biologic agents do not impact the Th1 / IL-12 / IFN- γ pathway and therefore may be less likely to exert a greater long-term benefit over GC for suppression of chronic inflammation in GCA mediated by the Th1 cell subset. Results from the small open-label study evaluating ustekinumab have shown initial promise [29]. These preliminary findings may further underscore the importance of blocking aspects of both Th cell lineages involved in the pathogenesis of GCA. To date interruption of the intracellular signaling upregulated by proinflammatory extracellular cytokines has not been pursued in patients with GCA.

Collaborative efforts between the Mayo Clinic vasculitis group and Drs. [name] and [name] have identified the importance of signal transducer and activator of transcription (STAT) transcripts in GCA [30]. Human temporal arteries were implanted in immunodeficient mice and peripheral blood mononuclear cells from patients with GCA were used to reconstitute the murine immune system. In the arterial lesional tissue, STAT-1 transcripts were notably abundant. IFN- γ , the major cytokine inducer of STAT-1, was also 10-fold higher than in age-matched non-GCA controls. Treatment with high-dose dexamethasone reduced IL-6 and IL-1 β expression but did not affect Th1 cell accumulation in the vessel wall or decrease IFN- γ production. However, treatment with tofacitinib, a Janus kinase (JAK)/STAT inhibitor, effectively

prevented Th1 cell accumulation in the vessel wall and decreased circulating levels of IFN- γ by 65%. This proof-of-concept study demonstrates that JAK/STAT inhibition can lead to reprogramming of T cell trafficking and prevent T cells from infiltrating the arterial wall, an effect that has not yet been observed with other therapeutic agents in this condition.

3.5. Baricitinib in Autoimmune Disease

Extracellular cytokines bind to cell-surface receptors which then generate downstream signaling through the activation of tyrosine kinases, including JAK. Cytokines induce JAK enzymatic activity by binding to the extracellular portion of their associated receptors, leading to activation of the receptor and initiation of intracellular signaling cascades. STATs, which reside in the cytosol, when stimulated by cytokines bind active phosphorylated receptors and are then in turn phosphorylated by JAKs. This leads to STATs translocating to the nucleus where they bind DNA and activate transcription. Exaggerated, aberrant, or protracted JAK/STAT signaling has been implicated in several autoimmune diseases and therefore provides potential targets for disease modification [31]. Indeed tofacitinib (JAK3 preferential inhibitor) has already been approved for use in rheumatoid arthritis and baricitinib has shown preliminary efficacy in rheumatoid arthritis [32-34], psoriasis [35] and alopecia areata [36].

3.6. Baricitinib in Giant Cell Arteritis

Cytokines and mediators that have been associated with aberrant autoimmunity and increased inflammatory responses in GCA include IL-6, IL-12, IL-23, and interferon γ (IFN- γ). These cytokines signal through the JAK family (JAK1, JAK2, JAK3 and tyrosine kinase 2 [Tyk2]) [37]. Baricitinib is an oral Janus kinase inhibitor with preferential inhibition of JAK1 and JAK2. IL-6 and IFN- γ primarily signal through JAK1 and IL-12 and IL-23 through JAK2. Therefore an agent that preferentially inhibits both JAK1 and JAK2 will provide reduction of intracellular signaling through multiple proinflammatory pathways, reducing activity of both pathologic Th17 and Th1 cell lineages.

Given these findings, an open-label phase II trial of baricitinib in patients with relapsing GCA is proposed. The purpose of this study will be to evaluate the safety and preliminary efficacy of baricitinib in treatment of patients with relapsing GCA.

4. OBJECTIVE(S) and ENDPOINT(S)

Objectives	Endpoints/Measures
Primary	

 To investigate the safety of baricitinib, 4 mg oral daily for duration of 52 weeks, administered to patients with relapsing GCA in combination with a standardized glucocorticoid taper 	
 Incidence of adverse effects and serious adverse effects, changes in hematology and clinical chemistry patterns
Secondary	

 To evaluate preliminary efficacy of baricitinib, 4 mg oral daily for duration of 52 weeks, administered to patients with relapsing GCA in combination with a standardized glucocorticoid taper 	
 Relapse-free survival at week 52 Relapse-free survival at week 24 Duration of glucocorticoid-free remission

	
 • Duration of glucocorticoid-free remission • Number of relapses per subject over time • Change from baseline erythrocyte sedimentation rate to end of study • Change from baseline C-reactive protein to end of study • Glucocorticoid dose (mg) at week 52 compared to baseline • Change in BVAS from baseline to end of study
--	---

[figure not shown]
5. STUDY DESIGN

5.1.1. Study Definitions

- **Active Disease:** ongoing signs or symptoms attributable to GCA accompanied by an elevated ESR ≥ 30 mm/hour or CRP 10 mg/L.
- **Clinically stable:** improvement in or absence of ongoing signs or symptoms attributable to GCA as evidenced by reduction in symptoms and/or improvement in (or normalization of) inflammatory markers
- **Relapse:** the recurrence of signs or symptoms (i.e. active disease) attributable to GCA in subject previously in remission
- **Remission:** the absence of signs or symptoms attributable to GCA and normalization of erythrocyte sedimentation rate (<30 mm/hour) and C-reactive protein (<10 mg/L).
- **Glucocorticoid-free remission:** the absence of signs or symptoms attributable to GCA following discontinuation of glucocorticoids
- **Signs and symptoms of GCA:** fronto-temporal headache; scalp tenderness; abnormality of temporal artery (tenderness, nodularity, decreased pulse); jaw, arm or leg claudication; polymyalgia rheumatica; vision change (blurring, diplopia); transient (amaurosis fugax) or permanent vision loss.

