5.4. Type and Number of Subjects

The study population will be comprised of 15 subjects with GCA who have experienced a relapse, determined by demonstrating active disease, within 6 weeks of baseline. Active disease will be defined as showing evidence of signs or symptoms attributable to GCA and the presence of either an ESR \geq 30 mm/hr or a CRP \geq 10 mg/L. Subjects demonstrating symptoms of visual manifestations (i.e. double vision, transient or permanent partial/complete vision loss), cerebrovascular compromise (ischemic stroke deemed secondary to GCA), or limb ischemia will be ineligible for enrollment. Patients on glucocorticoids for \geq 4 years consecutively (without interruption of more than 1 month) will be excluded to avoid issues with precipitating secondary adrenal insufficiency and/or symptoms of steroid withdrawal from an accelerated standardized glucocorticoid taper.

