7. SELECTION OF STUDY POPULATION AND WITHDRAWAL CRITERIA

7.1 Inclusion Criteria

Subjects are eligible for enrollment in the study if the following inclusion criteria are met:

1. Diagnosis of GCA defined by the following Revised GCA Diagnosis Criteria:

- Age ≥ 50 years.
- History of ESR ≥ 50 mm/hour or CRP ≥ 10 mg/L.
- Presence of at least **one** of the following:
 - Unequivocal cranial symptoms of GCA (new onset localized headache, scalp or temporal artery tenderness, otherwise unexplained mouth or jaw pain upon mastication).
 - Unequivocal symptoms of PMR, defined as shoulder and/or hip girdle pain associated with inflammatory stiffness.
 - Systemic inflammatory disease in which the presence of the fever (>38 degrees Celsius for ≥ 7 days), weight loss (> 5 lbs or 10% pre-morbid weight), and/or night sweats were attributable to GCA and no other cause was identified.
- Presence of at least **one** of the following:
 - Temporal artery biopsy revealing features of GCA.
 - Evidence of large-vessel vasculitis by angiography or cross-sectional imaging, including but not limited to magnetic resonance angiography (MRA), computed tomography angiography (CTA), positron emission tomography-computed tomography (PET-CT) or evidence of large-vessel or temporal artery vasculitis by ultrasound (US).

2. Relapse with active GCA within 6 weeks of study entry where active disease is defined by an ESR ≥ 30 mm/hr or CRP ≥ 10 mg/L AND the presence of at least **one**

of the following:

- Unequivocal cranial symptoms of GCA (new onset or recurrent localized headache, scalp or temporal artery tenderness, otherwise unexplained mouth or jaw pain upon mastication [i.e., jaw claudication]).
- Unequivocal symptoms of PMR, defined as shoulder and/or hip girdle pain associated with inflammatory stiffness.
- Other feature(s) judged by the clinician investigator to be consistent with GCA or PMR flares (e.g. fever of unknown origin, weight loss, fatigue/malaise, etc.)

3. Clinically stable at baseline visit (study drug initiation) such that the subject is able to safely participate in the standardized taper regimen in the opinion of the investigator.

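### Read literally, the relapse definition omits symptomatic flares with normal ESR and CRP, and possibly worsening of symptoms that never cleared; a sensitivity analysis would show how much depends on it

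*Combined protocol and SAP*

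**What the plan says.** The terms in Section 5.1.1 interlock:

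- Relapse is "the recurrence of signs or symptoms (i.e. active disease) attributable to GCA in subject previously in remission".
- Active disease is "ongoing signs or symptoms attributable to GCA accompanied by an elevated ESR" (30 mm/hour or more) or a CRP of 10 mg/L.
- Remission is "the absence of signs or symptoms attributable to GCA and normalization of erythrocyte sedimentation rate" (below 30 mm/hour) and CRP (below 10 mg/L).
- Clinically stable is "improvement in or absence of ongoing signs or symptoms attributable to GCA as evidenced by reduction in symptoms and/or improvement in" inflammatory markers.
- Glucocorticoid-free remission is "the absence of signs or symptoms attributable to GCA following discontinuation of glucocorticoids", with no marker condition.

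Section 5.2 and inclusion criterion 3 (Section 7.1) ask for clinical stability at baseline, not remission. For the entry relapse, Section 5.4 speaks of subjects who have "experienced a relapse, determined by demonstrating active disease, within 6 weeks of baseline" and attaches the same marker condition. Criterion 2 does likewise: "Relapse with active GCA within 6 weeks of study entry where active disease is defined by an ESR" or CRP threshold, plus a clinical feature.

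Section 9.8 assesses efficacy from signs, symptoms, ESR and CRP, and sets no threshold for an on-study event. Section 14 applies Kaplan-Meier methods to relapse-free survival and to duration of glucocorticoid-free remission, without defining event or censoring for either. Section 13 says efficacy would be evidenced by 10 of 15 subjects staying relapse-free.

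**The concern.** Relapse is the event behind four reported results: relapse-free survival at week 24 and at week 52, relapses per subject, and the 10-of-15 statement. Two kinds of clinical failure may fall outside it.

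The first is a symptomatic flare with normal markers. Section 2 expects baricitinib to show efficacy partly by lowering inflammatory markers. The drug could therefore affect the marker half of the event definition separately from the symptoms.

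The second is a subject who enters improved but still symptomatic, never clears, and then worsens. It is unclear whether that is a recurrence.

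Subjects of either kind could be carried as relapse-free or censored at a time related to their disease. Both would make disease control look better than it was, in data that Section 5.5 intends as support for a possible randomized trial.

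**Working it through.** **Step 1: apply the definitions to three cases.**

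| Case | Relapse, literal 5.1.1 | Relapse, symptoms-only reading | Glucocorticoid-free remission |
|---|---|---|---|
| A. Remits; symptoms return with raised ESR or CRP | Yes | Yes | Ends, if off prednisone |
| B. Remits; symptoms return with ESR <30 and CRP <10 | No | Yes | Ends, if off prednisone |
| C. Improved at week 0; symptoms never clear, then worsen with raised markers | Unclear | Unclear | Never starts |

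Case B turns on whether the words in brackets in the relapse definition are a condition or a loose gloss. Case C turns on whether a remission before the qualifying relapse counts, and on whether worsening without clearance is a recurrence.

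**Step 2: when can B split the two endpoints?** In Table 1 prednisone reaches 0 at week 15, 19 or 22 for the 10, 20 and 30 mg tiers. For subjects on schedule, both endpoints then run together for 52 − 15 = 37, 52 − 19 = 33 or 52 − 22 = 30 weeks. This is the window for disagreement, not its frequency.

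**Step 3: reproduce the plan's figure.** Section 13 gives n = 15, an expected rate of 30%, a one-sided level of 0.05, and 80% power for a 37-point gain.

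P(X ≥ r) = Σ (k = r to 15) C(15,k) p^k (1 − p)^(15−k)

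At p = 0.30, P(X ≥ 8) = 0.05001 and P(X ≥ 9) = 0.0152, so the critical count is 9. At p = 0.67, P(X ≥ 9) = 0.805. The stated 80% is reproduced.

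**Step 4: leverage of single subjects.** Start from 10/15 and reclassify one subject at a time.

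| Relapse-free | Exact 95% CI | One-sided 95% lower limit | One-sided P against 30% |
|---|---|---|---|
| 10/15 (67%) | 38.4–88.2% | 42.3% | 0.004 |
| 9/15 (60%) | 32.3–83.7% | 36.0% | 0.015 |
| 8/15 (53%) | 26.6–78.7% | 30.0% | 0.050 |
| 7/15 (47%) | 21.3–73.4% | 24.4% | 0.131 |

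Two reclassified subjects bring the result to the 0.05 line (0.05001 unrounded).

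**Step 5: illustration on assumed shares.** Suppose the true rate is 30% and a share f of true failures is counted as relapse-free. The apparent rate is 0.30 + 0.70f. The documents give no value for f.

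| f | Apparent rate | P(X ≥ 10) |
|---|---|---|
| 0 | 0.300 | 0.4% |
| 5% | 0.335 | 0.9% |
| 10% | 0.370 | 1.9% |
| 15% | 0.405 | 3.7% |
| 20% | 0.440 | 6.6% |

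The chance of reaching 10/15 passes 5% only at f of about 17.5%.

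**The case against.** The strongest reply is that the definition must be read the same way throughout. Criterion 2 requires a relapse. If that is the defined term, every enrolled subject has already been in remission, and the phrase carries no time limit. This stands to a large extent. A reader might infer that subjects who never remit on study certainly have no relapse event, and the documents do not support that. What remains is narrower: whether worsening of symptoms that never cleared is a recurrence.

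Secondly, requiring a raised marker is a defensible guard against subjective events in an open-label study, where the quick taper may itself cause withdrawal symptoms (Section 6.2), and it matches the entry rule. That also stands, and it is why the current definition should be kept. It does not remove the need to show what the marker condition leaves out.

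Thirdly, a reader might see a contradiction because one flare can end glucocorticoid-free remission and leave the subject relapse-free. Two endpoints may differ by design, and under a symptoms-only reading they agree here. The difference needs explaining, but it is not an error in itself.

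Fourthly, a reader might infer bias against the 30% benchmark. The documents do not give the relapse definitions behind that figure, and similar definitions could cancel the effect.

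Finally, Section 14 already reports sustained remission with exact intervals, plus ESR, CRP, BVAS and prednisone dose. These are partial safeguards. Sustained remission is not defined, and none of these measures enters relapse-free survival or the 10-of-15 statement. Step 4 would also hold for any cause of misclassification in 15 subjects.

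**Conclusion.** The point holds as an ambiguity with a known direction and an unknown size. Under the literal reading, marker-normal symptomatic flares are not relapses, and worsening of never-cleared symptoms may not be. The relapse-based results could then overstate disease control. Under a symptoms-only reading the first gap closes.

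The two-subject shift from P = 0.004 to P = 0.050 shows only how sensitive a 15-subject proportion is. The illustration rests wholly on assumed shares and on a 30% rate free of the same gap. Section 14 plans no hypothesis tests, efficacy is secondary and descriptive, and the primary safety objective is unaffected. This is a cheap improvement of low priority.

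**What to change.** Keep the current definition and the Kaplan-Meier estimate, and add to Section 14:

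1. One sensitivity analysis of relapse-free survival and of the 10-of-15 proportion. The event is the first investigator-attributed new or worsening GCA signs or symptoms after week 0, whatever the ESR and CRP and whether or not remission came first. It applies alike to all subjects.
2. The proportion of all treated subjects (15 as planned), with an exact 95% CI, who met the 5.1.1 remission definition by week 24 and by week 52 and had no relapse at any time since week 0. Subjects who leave early without relapse count as non-successes in this figure and are also listed separately. So are symptom-free subjects whose markers stay raised for a documented non-GCA reason. State how many subjects were in remission at week 0.

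Read the 10-of-15 statement beside both. Marker-normal flares after remission are caught by item 1, not item 2.

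The sponsor should also reconcile how relapse, glucocorticoid-free remission and disease worsening are used in Sections 5.1.1, 5.2 and 10.2. Relapse governs conduct there as well, and worsening has no endpoint status. No clinical rule is proposed.

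Cost: SAP wording, plus recording the date and GCA attribution of symptoms at existing visits, because Table 2 lists no separate relapse or symptom form. ESR, CRP and BVAS are already scheduled at week 0 and every later visit. The added figures may be lower and less comparable with the 30% benchmark. Item 1 may count some steroid-withdrawal symptoms and rests on open-label judgement, so it should remain a sensitivity analysis.
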